3.6. Treatments

After randomization, participants will receive a single 300 mg dose (up to 3 mL) of ADG20, or matching placebo, administered via IM injection.

3.7. Dose Adjustment/Modifications

As only a single dose is administered to each participant, there are no subsequent dose adjustments and/or modifications.

4. GENERAL STATISTICAL CONSIDERATIONS

4.1. General Rules and Considerations

Continuous variables will be summarized using the following descriptive summary statistics: the number of participants (n), mean, SD, median, first and third quartiles, minimum (min), and maximum (max).

Categorical variables will be summarized using frequency counts and percentages.

Baseline value, unless specified otherwise, is defined as the last non-missing measurement (scheduled or unscheduled) collected on or before the dose of study drug. If the date of dosing is missing, the date of randomization will be used instead.

Unless otherwise specified, the display precision for the summary statistics of all numerical variables will follow programming standards. Please see [Appendix A](#) for variable display standards.

When count data are presented, the percentage will be suppressed when the count is zero in order to draw attention to the non-zero counts. A row denoted “Missing” will be included in count tabulations as needed to account for dropouts and missing values. The denominator for all percentages will be the number of participants in the treatment group within the analysis set of interest, unless otherwise specified.

Change from baseline is defined as the value at the post-baseline visit minus the value at the baseline visit.

Study Day 1 is the calendar day that study drug is administered. Subsequent study days are calculated as the date of assessment/event – date of injection + 1. If a participant is not dosed, the date of randomization is used to define Study Day rather than the date of injection.

Time-to-event variables are defined from the date of dosing. If a participant is not dosed, the date of randomization is used.

All summaries involving diary data will be based on distinct diary date entries.

Unscheduled visits: Unscheduled visit measurements will be included in the analysis as follows:

- In scheduled visit windows per specified visit windowing rules.
- In the derivation of baseline measurements.
- In the derivation of maximum/minimum change from baseline values and worst post-baseline values for safety analyses.
- In individual participant data listings as appropriate.

Visit windowing rules: Assessments collected on the nominal visits per the protocol schedule will be included in by-visit summaries and analysis. If an assessment is missing from a nominal visit, available assessments from the unscheduled visits within the protocol-defined target-study-day range may be mapped to the corresponding nominal visit. The assessment occurring closest to the target study day will be used. If there are multiple assessments equally distant to the target study day, the earliest assessment will be used.

All diary data will be summarized based on the actual day.

Incomplete/missing data:

Imputation rules for missing dates of prior/concomitant medications, including COVID-19 vaccinations and prohibited medications, and procedures are provided in [Appendix C](#).

Imputation rules for missing AE are provided in [Appendix D](#).

Data that are continuous in nature but are reported in the form $< x$, $> x$, $\leq x$, or $\geq x$ (where x is considered as the limit of quantitation) will be set to limit of quantitation value with the following exceptions:

- For viral load data:
 - Viral load values reported as detected but BLQ of the PCR assay (<714 copies/mL) are imputed with half of LLOQ of the PCR assay (ie, 357 copies/mL)
 - Viral load values reported as not detected are imputed with 1 copy/mL (ie, $0 \log_{10}$ copies/mL)
 - All viral load analyses will use both observed and imputed viral load data. Listings present both observed and imputed viral load.
- For PK concentrations
 - Serum concentrations that are BLQ will be treated as zero for PK analyses, except for BLQ values observed between 2 quantifiable concentrations, which will be set to missing. If consecutive BLQ concentrations are followed by quantifiable concentrations in the terminal phase, those concentrations after BLQ concentrations will be treated as missing. Missing concentrations will be treated as missing in the PK parameter calculations.
- Efficacy endpoint data will be imputed as detailed in Section [5.5](#).
- Other incomplete/missing data will not be imputed, unless specified otherwise.

Treatment groups: The following treatment groups will be used for summary purposes:
ADG20, Placebo

All analyses and data summaries/displays for efficacy will be provided by treatment group using the appropriate analysis population unless otherwise specified.

Individual participant listings of all data represented on the eCRFs and laboratory data will be provided to facilitate the investigation of tabulated values and to allow for the clinical review of all efficacy and safety data. All data listings and tables displaying participant data that contain an evaluation date will display study day. Listings will be sorted by Subject ID and treatment.

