4.2.2. Premature Withdrawal from the Study

Participants may withdraw from the study at any time and for any reason, without prejudice to their future medical care, by the investigator or at the study site. Every effort should be made to keep participants in the study.

A participant will be considered to have completed the study when the Month 14 Follow-up Visit is completed. If a participant/guardian/LAR/sponsor requests a participant to be withdrawn at any time after randomization into the study, the investigator will make every effort to encourage the participant to complete the Day 29 visit assessments (if prior to Day 29), Month 6 visit assessments (if after the Day 29 visit but before Month 6), or the Month 14 EOS visit assessments (if after the Month 6 visit is completed) as shown in [Table 12-1](#).

As permitted by local guidelines, survival status should be reported through Month 14 for participants who received study drug but withdrew from study participation, including survival status or death available via public records (eg, death certificates or public registers), medical records, participant, or participant contacts, unless the participant has expressly withdrawn consent for survival follow up.

If a participant/guardian/LAR/sponsor chooses to withdraw a participant from the study prior to completion, the investigator must be informed immediately and the reason for withdrawal is to be recorded in the eCRF. The primary reason for premature withdrawal from the study should be selected from the following standard categories:

Death: The participant died.

Participant's Request: The participant is unable to continue to participate in the study but does not withdraw consent. If the participant gives a reason, this reason must be recorded in the eCRF.

Withdrawal of Consent: The participant desired to withdraw from further participation in the study absence an investigator-determined medical need to withdraw. If the participant gave a reason for withdrawing, it must be recorded in the eCRF.

Note: If the participant withdraws consent for disclosure of future information, the sponsor may retain, and continue to use, any data collected before such a withdrawal of consent. If a

participant withdraws from the study, they may request destruction of any samples taken that were not tested, and the investigator must document this in the site study records.

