5.5.9. Post-Acute Sequelae of SARS-CoV-2 Infection

During the long-term follow-up period, participants will be asked questions about their overall health status including return to usual health and usual activities and any ongoing symptoms associated with COVID-19 at the visits specified in the Schedule of Events ([Appendix M](#)). Symptoms reported on the Long-term Health Status Assessment eCRF will be considered PASC events. The number and percentage of participants with any PASC will be summarized by treatment group and in those participants with and without a COVID-19-related hospitalization through Day 29 with respect to the mFAS-non-Omicron. The number and percentage of participants reporting each symptom thought to be related to COVID-19 and the number and percentage of participants returning and not returning to usual health and usual activities will be summarized by treatment arm. The number of participants in each arm reporting no symptoms, 1 ongoing symptom and >1 ongoing symptom will be summarized at Day 60, Day 90, and Month 6. The overall severity of PASC symptoms will be presented (absent, mild, moderate, severe) by treatment arm and time point (Day 60, Day 90, and Month 6).

These data will also be presented in a listing.

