APPENDIX B. ANALYSIS VISIT WINDOWS

Assessments collected at scheduled or unscheduled visits will be mapped using the analysis visit windows listed in [Table 10](#). All diary data will be analyzed using the actual day. Refer also to Section [4.1](#).

Table 10: Analysis Windows

AVISIT	AVISITN	Range of Trial Day	Target Day	If more than one value, which value is used for analyses
Screening	1	Day -2 to 1		Last value prior to administration of study drug
Day 1	2	Day 1	Day 1	Day 1
Day 3	4	Day 2 to Day 4	Day 3	Nominal visit. If none exist, then closest to target day.
Day 5	6	Day 4 to Day 6	Day 5	Nominal visit. If none exist, then closest to target day.
Day 7	8	Day 6 to Day 8	Day 7	Nominal visit. If none exist, then closest to target day.
Day 11	12	Day 9 to Day 13	Day 11	Nominal visit. If none exist, then closest to target day.
Day 14	15	Day 12 to Day 16	Day 14	Nominal visit. If none exist, then closest to target day.
Day 21	22	Day 18 to Day 23	Day 21	Nominal visit. If none exist, then closest to target day.
Day 29	30	Day 24 to Day 34	Day 29	Nominal visit. If none exist, then closest to target day.
Day 60	31	Day 53 to Day 67	Day 60	Nominal visit. If none exist, then closest to target day.
Day 90	32	Day 76 to Day 104	Day 90	Nominal visit. If none exist, then closest to target day.
Month 6	33	Day 150 to Day 210	Day 180	Nominal visit. If none exist, then closest to target day.
Month 11	34	Day 300 to Day 360	Day 330	Nominal visit. If none exist, then closest to target day.
Month 14	35	Day 360 to Day 480	Day 420	Nominal visit. If none exist, then closest to target day.

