Review of COVID-19 Symptom Diary, reported vitals, ISR diary, & COVID-19 severity assessment (Day 1 assessment should be completed prior to study drug administration)		X	X	X	X	X	X	X	X					
Survival assessment & Medically Attended Visits assessment ^k			X	X	X	X	X	X	X	X	X	X	X	X
Collect/update participant contacts		X			X					X	X	X	X	X
Long-term health status assessment											X	X	X	
Household transmission questionnaire										X				
Participant At-Home Assessments/Collections														
Day 1 assessments/collections by participant will be observed by site staff prior to study drug administration; Days 1-4: ISR diary for IM injection participants.														
Saliva sample for SARS-CoV-2 RT-qPCR ^l		X	X	X	X	X	X	X	X					
Daily COVID-19 Symptom Diary & ISR Diary ⁱ		X				X								
Daily temperature, SpO ₂ , heart rate ^m		X			X									

ADA=anti-drug antibodies; EOS=end-of-study; ISR=injection site reaction; RT-qPCR=quantitative reverse transcription polymerase chain reaction; SpO₂=oxygen saturation; WOCBP=women of childbearing potential.

^a Note that screening procedures may occur on the same day of dosing on Day 1. Study Day 1 is the calendar day that study drug is administered. On Day 1, all study procedures except ISR diary completion and collection of participant contacts are to be performed prior to study drug administration. Adverse events occurring from when the participant signs the ICF until the Month 14 (EOS) visit or withdrawal will be recorded. Any screening inclusion criteria with laboratory values associated (eg, eGFR, FSH, etc) should be based on local laboratory results or most recent medical record.

^b If a participant/guardian/LAR requests a participant to be withdrawn at any time after randomization into the study, the investigator will make every effort to encourage the participant to complete the Day 29 assessments (if prior to Day 29), Month 6 visit assessments (if after the Day 29 visit but before Month 6), or the Month 14 EOS visit assessments (if after the Month 6 Visit completed).

^c Visits after Day 1 may not be combined. Visit codes: C (in-clinic); C/H (in-clinic or home health); T (Telemedicine, 'T' visits may also be in-clinic or home health).

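### SAP 4.1 and Appendix B disagree on where to file a Day 29 or Month 6 visit done early because of withdrawal, so some by-visit results can include mistimed data

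*SAP*

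**What the plan says.** **Withdrawal visits.** Protocol 4.2.2 asks the investigator to "encourage the participant to complete the Day 29 visit assessments (if prior to Day 29), Month 6 visit assessments" and so on to Month 14, according to when the participant leaves. Footnote b to the SAP schedule (Appendix M) repeats the rule: "complete the Day 29 assessments (if prior to Day 29), Month 6 visit assessments (if after the Day 29 visit but before Month 6". Neither schedule has a separate early-termination column.

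**SAP 4.1.** "Assessments collected on the nominal visits per the protocol schedule will be included in by-visit summaries and analysis". The next rule concerns a missing nominal assessment: "available assessments from the unscheduled visits within the protocol-defined target-study-day range may be mapped to the corresponding nominal visit". The day range is attached to unscheduled visits only.

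**SAP Appendix B.** "Assessments collected at scheduled or unscheduled visits will be mapped using the analysis visit windows" of Table 10. The ranges are Days 24 to 34 for Day 29 and Days 150 to 210 for Month 6. A further column, for use when there is more than one value, reads "Nominal visit. If none exist, then closest to target day". Appendix B refers the reader back to 4.1.

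**PASC.** SAP 5.5.9 states "Symptoms reported on the Long-term Health Status Assessment eCRF will be considered PASC events" and reports them at Day 60, Day 90 and Month 6.

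No section mentions early-termination assessments in connection with visit mapping.

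**The concern.** The withdrawal procedure can produce visits that carry a late label but were done early. The SAP has two rules for such a visit and they give different answers. A programmer who follows 4.1 keeps the label; one who follows Appendix B uses the study day.

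Under the first choice, acute-phase data are reported as late follow-up. The exposed results are:

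- the saliva viral-load change at Day 29, where the repeated-measures model uses whatever data are available at each time point;
- the viral-load AUC, which is calculated only if a Day 29 value exists;
- PASC at Month 6, since any symptom on the long-term form counts;
- by-visit laboratory and vital-sign summaries (the changes through Day 29 belong to the primary safety objective), ADA by visit, and PK concentrations by time point.

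**Working it through.** The plan states no figure on this point, so the check is to file the same visit under each rule.

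**Inputs.** Table 10 ranges (SAP Appendix B): Day 3, 2–4; Day 5, 4–6; Day 7, 6–8; Day 11, 9–13; Day 14, 12–16; Day 21, 18–23; Day 29, 24–34; Day 60, 53–67; Day 90, 76–104; Month 6, 150–210. Half-life of about 97 days (Protocol 1.1). AUC missing-data rule (SAP Table 4).

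**1. Same visit, two results.**

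| Label | Day done | SAP 4.1 alone | Table 10 range |
|---|---|---|---|
| Day 29 | 8 | Day 29 | Day 7 |
| Day 29 | 10 | Day 29 | Day 11 |
| Day 29 | 17 | Day 29 | none |
| Month 6 | 40 | Month 6 | none |
| Month 6 | 90 | Month 6 | Day 90 |

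**2. How often the rules differ, counted over possible days.**

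- Day 29 label: the possible early days are 2 to 28, which is 27 days. Days 2 to 23 lie outside 24–34, which is 22 days. Of these, 21 fall in an earlier range and one (Day 17) in none.
- Month 6 label: the possible early days are 30 to 179, which is 150 days. Days 30 to 149 lie outside 150–210, which is 120 days. Those in an earlier range are Days 30–34 (5), 53–67 (15) and 76–104 (29): 5 + 15 + 29 = 49. The other 120 − 49 = 71 fall in none.

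These are counts of calendar days, not of participants.

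**3. AUC.** Saliva is scheduled on Days 1, 3, 5, 7, 11, 14, 21 and 29. No AUC is calculated if Day 1 or Day 29 is missing, or if more than three values are missing. A participant who leaves on Day 8 with all earlier samples, and gives a sample labelled Day 29, lacks exactly Days 11, 14 and 21. That is three, so an AUC is calculated. If the viral load is v at both Day 7 and withdrawal, the last trapezoid is (29 − 7) × v = 22v on nominal days, against (8 − 7) × v = v on actual days. With v = 4 log10 copies/mL (an assumption), that is 88 against 4 log10-days. If actual days were used in the trapezoid, the result would be an area over 7 days reported as one over 28.

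**4. PK concentration.** Assuming log-linear decline from day d, the ratio of a sample taken on day d to the same participant's Day 180 level is 2^((180 − d)/97). For d = 40, 2^(140/97) = 2.72. For d = 60, 2^(120/97) = 2.36. The effect on a Month 6 mean depends on the share of such samples, which is not given. At an assumed 1% it is 0.01 × (2.72 − 1) = 1.7%; at 5% it is 8.6%.

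**5. Results that do not depend on the visit label.**

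- Primary endpoint: defined by admission or death date (SAP 3.5.1).
- Diary endpoints: analysed by actual day (SAP 4.1).
- Saliva viral clearance: participants who discontinue before Day 29 count as not cleared (SAP 3.5.2).
- PK parameters: actual sampling times (SAP 6.3).

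**The case against.** The strongest reply is that Appendix B already settles the matter. It covers scheduled visits by name, a Day 8 sample lies outside Days 24 to 34, and the nominal-visit preference sits in a column for choosing among several values, so it is naturally a tie-break inside the range and not an override of it. The laboratory and vital-sign sections (SAP 5.8.3 and 5.8.4) cite Appendix B.

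Much of this stands. A reader might infer that the SAP analyses nominal visits whatever the study day. The documents do not support that as a settled fact; it is what 4.1 says when read alone. But Appendix B points back to 4.1, neither is given precedence, and 5.8.3 and 5.8.4 cite it only for unscheduled and multiple in-window values, which does not describe a single nominal visit outside its window.

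It is also fair that the protocol only encourages these assessments, and does not say that they take place on the day of withdrawal or how they are labelled in the eCRF. That they carry the Day 29 or Month 6 label is an inference from the absence of any other column.

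Two wider readings fail:

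- **Month 14.** The SAP lists no laboratory, site vital-sign, PK, ADA or viral sample at that visit, so no by-visit sample can be misplaced.
- **Time to symptom resolution**, a tested key secondary endpoint. A reader might infer that an early Day 29 visit moves censoring to Day 30. SAP 3.5.1 already censors participants who discontinue at last contact.

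Finally, some exposure is narrow. Treatment-emergent ADA counts any post-baseline visit, so only the by-visit ADA table is sensitive. Day 29 saliva change is in the analysis table but not in the endpoint list, which stops at Day 14. The AUC example needs all of Days 1, 3, 5 and 7.

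**Conclusion.** The point holds as an unresolved conflict between SAP 4.1 and Appendix B over nominal visits done outside their day range. Early-withdrawal visits are the foreseeable case. Under the 4.1 reading, the affected results would be mistimed by up to 27 days for the Day 29 label (29 − 2) and up to 150 days for the Month 6 label (180 − 30). Under the Appendix B reading they would not.

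The total bias cannot be sized, because the documents give neither the number of withdrawals nor how many would do an early milestone visit. Primary efficacy and the tested hierarchy are not at risk. The exposed efficacy results carry nominal p-values or are descriptive, and the safety summaries are descriptive. The conclusion assumes that early visits are recorded under the milestone label. It merits correction because one of the two stated rules gives wrong results and the choice would otherwise fall to the programmer.

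**What to change.** State in SAP 4.1, with a matching line in Appendix B:

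- The Table 10 day ranges govern all assessments, including nominal visits done early because of withdrawal.
- The nominal-visit preference applies only among values already inside the range.
- Assessments outside every range are listed but not used in by-visit summaries, as the Day 29 value for the repeated-measures model or the AUC, or as the Month 6 PASC assessment.

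Two details should be settled at the same time. Some ranges overlap (Day 4, Day 6, Days 12–13 and Day 360), so the text should say which visit takes an assessment on those days. It should also say what happens when the range belongs to a visit at which that test is not scheduled, such as a blood sample on Day 10; listing only would be consistent with the rest.

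The cost is a few sentences and a programmed check of visit date against Table 10, made before unblinding for the Day 29 analysis. The downside is slightly fewer Day 29 and Month 6 values.

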4.2. Sample Size

The primary analysis is the comparison of the ADG20 arm versus the placebo arm with respect to proportion of participants infected with a non-Omicron variant of SARS-CoV-2 with a COVID-19-related hospitalization or all-cause death through Day 29.

The original required sample size was calculated based on the following assumptions obtained from a review of data from studies of other mAbs in participants with a high risk for disease progression leading to hospitalization or death prior to widespread emergence of both the Delta and Omicron variants ([AstraZeneca 2022](#); [Eli Lilly and Company 2022](#); [GlaxoSmithKline 2021](#); [Regeneron 2022](#)). The original sample size of 1084 participants was planned with 90% power, 2-sided alpha .05, and a 1:1 randomization ratio to detect a statistically significant risk reduction with a true efficacy of relative risk reduction 70% and a 5% event rate in the placebo arm.

At the time of enrollment suspension in January 2022, a total of 399 participants were randomized. Of them, approximately 320 participants will be included in the primary efficacy population of participants with a non-Omicron variant of SARS-CoV-2. Based on blinded monitoring of the primary endpoint outcomes, an aggregate event rate of approximately 9% was observed, indicating a higher placebo event rate than previously assumed and providing approximately 80% power to test the primary endpoint in the primary efficacy population given an estimated placebo event rate of 12% and the same efficacy assumption.

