At the time of enrollment suspension in January 2022, a total of 399 participants were randomized. Of them, approximately 320 participants will be included in the primary efficacy population of participants with a non-Omicron variant of SARS-CoV-2. Based on blinded monitoring of the primary endpoint outcomes, an approximate aggregate event rate of 9% was observed, indicating a higher placebo event rate than previously assumed and providing approximately 80% power to test the primary endpoint in the primary efficacy population given the same efficacy assumption.

The analysis of the primary estimand, incidence of COVID-19-related hospitalization or all-cause death through Day 29 in the ADG20 arm versus the placebo arm in the mFAS-non-Omicron analysis set will be analyzed using the methodology for determining a standardized estimator for a binary outcome as detailed in Ge 2011, with adjustment for the following prognostic factors: age (continuous), sex (categorical), baseline qualitative serostatus (categorical), BMI (continuous), and baseline viral load (continuous). The standard error of the standardized estimator will be estimated using the delta method based on the algorithm presented in Ge 2011. The risk difference (placebo minus ADG20) with CI (using the Miettinen-Nurminen method), standardized risk difference with CI, relative risk reduction with CI, and associated p-value for the standardized risk difference will be provided. A treatment policy strategy will be used to handle intercurrent events of interest. For example, treatment effect will be estimated regardless of baseline or emergence of coinfection with a non-SARS-CoV-2 pathogen, which is a potential intercurrent event of interest.

The key secondary endpoints will be tested in the following order in the mFAS-non-Omicron analysis set: (1) Severe/critical COVID-19 or all-cause death through Day 29, (2) COVID-19-related emergency room visits, COVID-19-related hospitalization, or all-cause death through Day 29, and (3) Time to sustained resolution of COVID-19 symptoms through Day 29.

Analyses of other secondary and exploratory efficacy endpoints will be conducted to support the findings of the primary and key secondary efficacy endpoints.

Safety Analyses

Safety summaries through Day 29 and overall will be presented.

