7.1. Sample Size Determination

The primary analysis is the comparison of the ADG20 arm versus the placebo arm with respect to the proportion of participants infected with a non-Omicron variant of SARS-CoV-2 with a COVID-19-related hospitalization or all-cause death through Day 29.

The original sample size was calculated based on assumptions obtained from a review of data from studies of other mAbs in participants at high risk for disease progression leading to hospitalization or death prior to widespread emergence of both the Delta and Omicron variants

(AstraZeneca 2022; Eli Lilly and Company 2022a; GlaxoSmithKline 2022; Regeneron 2022). The original sample size of 1084 participants was planned with 90% power, 2-sided alpha .05, and a 1:1 randomization ratio to detect a statistically significant risk reduction with a true efficacy of relative risk reduction 70% and a 5% event rate in the placebo arm.

At the time of enrollment suspension in January 2022, a total of 399 participants were randomized. Of them, approximately 320 participants will be included in the primary efficacy population of participants with a non-Omicron variant of SARS-CoV-2. Based on blinded monitoring of the primary endpoint outcomes, an approximate aggregate event rate of 9% was observed, indicating a higher placebo event rate than previously assumed and providing approximately 80% power to test the primary endpoint in the primary efficacy population given the same efficacy assumption.

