4.4. Multiplicity Adjustments

To control the overall type I error rate at .05 (2-sided), a hierarchical testing procedure will be used, such that testing for the key secondary analyses difference will proceed only if the treatment difference is statistically significant in the primary analysis.

Analyses of the other secondary and exploratory endpoints will be conducted to support the findings of the primary and key secondary efficacy analyses without accounting for multiple comparisons. Nominal p-values and 95% CIs will be computed for these secondary and exploratory efficacy analyses when applicable.

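### Does the 80% power stated in SAP 4.2 conflict with the blinded 9% event rate cited beside it?

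*SAP*

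**What the plan says.** SAP Section 4.2 first gives the original design: "The original sample size of 1084 participants was planned with 90% power, 2-sided alpha .05, and a 1:1 randomization ratio", for "a true efficacy of relative risk reduction 70% and a 5% event rate in the placebo arm". It then says that 399 participants had been randomized when enrollment was suspended and that "approximately 320 participants will be included in the primary efficacy population of participants with a non-Omicron variant of SARS-CoV-2". From blinded monitoring of the primary endpoint, "an aggregate event rate of approximately 9% was observed". The section takes this as a sign that the placebo rate is above the 5% first assumed, and as "providing approximately 80% power to test the primary endpoint in the primary efficacy population given an estimated placebo event rate of 12" percent, under the same efficacy assumption.

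Protocol Section 7.1 gives the same 399, 320 and 9%, and ends with "providing approximately 80% power to test the primary endpoint in the primary efficacy population given the same efficacy assumption". The Efficacy Analyses part of the synopsis matches it: "an approximate aggregate event rate of 9% was observed, indicating a higher placebo event rate than previously assumed and providing approximately 80% power". Neither protocol text prints a revised placebo rate. Neither document says how 12% was obtained, or in which participants the 9% was observed.

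**The concern.** The sentence in SAP 4.2 reads as a chain: 9% was seen, so the placebo rate must be higher than planned, so power is about 80%. Under equal allocation, an aggregate rate and a relative risk reduction together fix both arm rates. Taking 9% and 70% gives a placebo rate near 13.8%, not 12%. Taking 12% and 70% gives an aggregate of 7.8%, not 9%. So two of the three printed numbers seem to exclude the third.

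The protocol looks worse on this point. With no 12% printed, a reader who works from 9%, 70% and 320 gets about 86%, not 80%.

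This is the only power statement for the reduced primary population. If it were wrong, the result would be read against the wrong planning assumptions. An overstated power would matter most, because a null result would then look more informative than it is.

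**Working it through.** **Inputs.** About 320 participants, taken as 160 per arm (assumes 1:1 carries over to the subset); placebo rate 12%; reduction 70%; blinded aggregate about 9% (all SAP 4.2). Two-sided alpha 0.05 (SAP 4.4). The documents name no power method. I use the unadjusted two-proportion formula with pooled null variance:

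power = Φ{ [ |p0 − p1| − 1.96·√(2p̄(1 − p̄)/n) ] / √[(p0(1 − p0) + p1(1 − p1))/n] }, with p̄ = (p0 + p1)/2.

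**1. Does the formula fit the sponsor's design?** For 5% versus 1.5% at 542 per arm it gives 90.2%, against the stated 90% for 1084. Solving for 90% gives N = 1076. It fits.

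**2. The SAP's figure.** p0 = 0.12, p1 = 0.3 × 0.12 = 0.036, p̄ = 0.078.
- Null term: 1.96 × √(2 × 0.078 × 0.922/160) = 0.0588
- Alternative SE: √[(0.1056 + 0.0347)/160] = 0.0296
- (0.084 − 0.0588)/0.0296 = 0.85, so power is **80.3%**

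The stated 80% reproduces.

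**3. Aggregate implied by 12% and 70%.** 0.12 × 1.3/2 = **7.8%**.

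**4. Power implied by 9% and 70%, if the 9% belongs to the 320.** p0 = 2 × 0.09/1.3 = 13.85%, p1 = 4.15%, power **86.1%**. An aggregate of 8.5% to 9.5% gives 83.9% to 88.1%, so on this reading rounding alone does not bring power down to 80%.

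**5. Dependence on method.**

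| Method | 12% vs 3.6% | 13.85% vs 4.15% |
|---|---|---|
| Pooled | 80.3% | 86.1% |
| Unpooled | 81.0% | 86.7% |
| Exact, chi-square test | 82.2% | 88.0% |
| Fisher exact | 76.7% | 83.9% |
| Continuity-corrected | 73.9% | 81.2% |

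The continuity-corrected formula would bring the protocol's inputs close to 80%. It also gives 73.9% for the SAP's inputs and 1188 for the original N, so it does not fit the rest.

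**6. If the 9% covers all 399.** The other 79 are then the Omicron group. SAP Section 1 expects little efficacy there. Assume, beyond what the documents state, a 12% rate in both arms of that group:

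(0.078 × 320 + 0.12 × 79)/399 = (24.96 + 9.48)/399 = **8.6%**, which rounds to 9%.

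To land between 8.5% and 9.5% overall, the 79 need a rate between (33.9 − 24.96)/79 = 11.3% and (37.9 − 24.96)/79 = 16.4%. A rate of 12% lies inside that range. If ADG20 were partly effective in those 79 and their rate fell below 11.3%, the match would fail.

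**7. If the 9% covers only the 320.** Expected events are 0.09 × 320 = 28.8 against 0.078 × 320 = 24.96, about four apart. The standard error of a 9% rate is √(0.09 × 0.91/320) = 1.6 points, and the gap is 1.2 points. With a true rate of 7.8%, the chance of 29 or more events is 0.23.

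**The case for a change.** The strongest objection is that the SAP does not present 12% as a free choice. It calls it an estimate, in the same sentence as the 9%, and gives no step from one to the other. Sampling error can make 7.8% and 9% compatible, but it does not explain how 12% was derived. Read with both rates taken literally, 12% on placebo and 9% overall put ADG20 at 6%, a reduction of only 50%, and power at 46.6%. Two rates that permit such a reading should not stand together unexplained, and the remedy would be only a few sentences.

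The missing derivation and the unnamed population are real omissions, and that part stands. The 50% reading does not, because the SAP explicitly keeps the original efficacy assumption. Nor is the planning placebo rate in doubt: the SAP prints 12%, and 13.8% appears in neither document.

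The protocol's silence carries less weight than it seems. Its Section 7 describes itself as brief and leaves detail to the SAP; both documents state the same 80%, and the SAP supplies the input that the protocol leaves out. An explanation also cannot be written in from outside, since no reason for choosing 12% is given anywhere. Restating power as 86% would raise the claim on the strength of a rate whose population is unknown. Editing the protocol would mean an amendment submitted to ethics committees (Protocol 10.13.1), for a study with enrollment suspended and none further expected.

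**Conclusion.** No change is needed. The 80% is correct for the inputs printed next to it: 80.3% at 160 per arm, 12% versus 3.6%, two-sided 0.05. What is missing is the link between 9% and 12%, and no printed figure is shown to be wrong by that. If the 9% refers to all 399 randomized, the numbers can agree after rounding (8.6%, on the assumption of a 12% rate in the other 79). If it refers to the 320, the gap is about four events, and at a 70% reduction the stated power is about six points too low rather than too high.

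The calculation had no decision left to inform: the suspension of enrollment fixed the sample size, and the primary test, its alpha and the testing order do not use the planning rate. The powers above are unadjusted approximations with an assumed equal split, whereas the planned test is a covariate-adjusted standardized risk difference. Spelling out the derivation would make the section easier to follow, but would change neither the trial nor the reading of its result.
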